PROTOCOL TITLE:

“Comparing the Effectiveness of Clinicians and Paraprofessionals to Reduce Disparities in Perinatal Depression.”

PRINCIPAL INVESTIGATOR:

S. [name]
Department of Medical Social Sciences
[contact]
[contact]

VERSION NUMBER:

Version 13

VERSION DATE:

July 3, 2018

1.0 Purpose of the Study:

There is considerable evidence that most perinatal women at risk for postpartum depression do not engage in mental health services, even when referred by home visiting (HV) programs, primary care physicians, obstetricians, or gynecologists (Zittel-Palamara et al., 2008). Thus, interventions that can be delivered via alternative settings—e.g., HV programs—are essential to prevent the onset of major depression and worsening of depressive symptoms among perinatal women. This PCORI funded project aims to evaluate whether the Mothers and Babies (MB) intervention, when led by paraprofessional home visitors, is more efficacious than usual care (i.e., home visiting without the MB enhancement). It will also examine if MB, when led by paraprofessional home visitors, is not inferior to MB delivered by mental health professionals. The results of this study will inform decision-making by HV programs regarding provision of MB to perinatal women at risk for developing major depression.

Study Aims:

Aim #1 is to conduct a superiority trial that compares the efficacy of MB delivered by paraprofessional home visitors versus usual care (i.e., home visiting without MB) on patient-reported outcomes, including depressive symptoms, quality of life, parenting practices, engagement in pleasant activities, and relationship with one's partner.

Aim #2 is to conduct a non-inferiority trial that compares the effectiveness of MB delivered by (a) mental health clinicians versus (b) paraprofessional home visitors.

Aim #3 is to evaluate whether effectiveness of the two versions of MB (clinician led vs. paraprofessional home visitor led) varies according to patient characteristics (e.g., race, ethnicity, first-time mother, and/or geographic type of home visiting (HV) program (i.e., urban vs. rural).

Aim #4 is to examine the feasibility and acceptability of MB delivered by paraprofessional home visitors and mental health clinicians.

2.0 Background / Literature Review / Rationale for the study:

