The post-intervention assessment consists of one depressive symptom measure, so no remuneration will be provided. Baseline and follow-up data will be collected and managed using REDCap (Research Electronic Data Capture), a secure web-based application designed to support data capture for research studies, hosted and supported by Northwestern’s Clinical and Translational Science Institute. Once research staff enters participant contact information, REDCap will generate emails or texts containing web-based survey links at scheduled time points. Baseline data will be collected within 2-3 weeks of establishing client eligibility and participation agreement. Women who do not complete the web-based baseline assessment in this timeframe will be contacted by phone by the Research Coordinator to complete the assessment either by phone or online, ensuring that baseline data are collected prior to the first MB group. Informed consent will be obtained prior to administering the baseline assessment. If a study participant decides that they do not want to consent to participate in this study, no data will be collected from this participant. For the post-intervention, 12-week postpartum, and 24-week postpartum assessments, study participants who do not complete web-based assessments within one week of the web link being sent to them will be contacted by the research team to complete the assessments by phone.

Table 4 describes this study’s outcome indicators, measures, and data collection timelines.

Outcome Indicator	Measure	Baseline	Post-Intervention	12 weeks postpartum	24 weeks postpartum
Depressive Symptoms	Edinburgh Postpartum Depression Scale	X			
Current & Lifetime Major Depressive Episode	Maternal Mood Screener (MMS)	X		X	X

DEPRESSION					
Depressive Symptoms*	Quick Inventory of Depressive	X	X	X	X
Symptomatology					
PROXIMAL OUTCOMES					
Behavioral Activation	Behavioral Activation	X		X	X
Pleasant Activities	Pleasant Activities Schedule	X		X	X
Mood Regulation	Negative Mood Regulation Scale	X		X	X
Social Support	MOS Social Support Survey	X		X	X
Decentering	Experiences Questionnaire	X		X	X
Relationship w/Partner	Dyadic Adjustment Scale	X		X	X
Responsive and Reactive Parenting	Parental Cognitions and Conduct toward the Infant Scale			X	X
Subjective Well-Being	Flourishing Scale	X		X	X
Perceived Stress	4-item Perceived Stress Scale	X		X	X
PRENATAL HEALTH BEHAVIORS					
DEMOGRAPHICS					
INTERVENTION SKILL USE					
INVOLVEMENT IN PRENATAL SERVICES					

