For our **non-inferiority (NI) analyses** (Aim 2) comparing MB led by home visitors vs. MB led by mental health clinicians, we used similar assumptions of a 6.0 SD on the QIDS-16. We will have >85% power to detect a difference in mean QIDS-16 scores of two points between the two arms with 1224 analyzable participants' data (i.e., 612 in each arm, or 18 clusters in each group with 34 participants on average) with an ICC no larger than .01. We have taken into consideration the potential loss of up to two clusters in each study arm for our NI analyses. Even with a loss of two clusters, which would leave us with 1064 analyzable participants' data (i.e., 532 in each arm), we will have >80% power to detect a difference in mean QIDS-16 scores of two points between study arms with an ICC no larger than .01. Since we recognize that power to claim NI will depend heavily on the magnitude of any ICC, we will perform several ICC calculations within each arm to assess power assumptions post hoc. We do not anticipate adequate power to claim NI regarding the incidence of new cases of major depression. If we assume 15% incidence in the professional arm versus 20% in the paraprofessional arm (i.e., a margin of NI of 5%), a sample size of 1224 participants would have 64% power and a sample size of 1064 would have >50% power at the 5% level of significance without accounting for any ICC. Thus, we will statistically compare the two arms with respect to MDD incidence, but do not anticipate the ability to claim NI.

15.0 Data Monitoring Plan to Ensure the Safety of Participants:

Any study participant who endorses thoughts of self-harm will be referred to the supervisor at the home visiting program, by the study coordinator. The supervisor, who is trained in responding to and addressing suicidal ideation, will use their agency's protocol to make a determination regarding whether the study participant is in danger of harming herself or others and will determine necessary steps to ensure the safety of the study participant. The Principal Investigator will be notified

immediately of any such referrals made by study staff. In addition, should administration of depression scale indicate the participant is experiencing severe depressive symptoms, the supervisor at the home visiting program will be notified in order to provide appropriate referrals for their client's mental health treatment linkage.

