We will administer the Maternal Mood Screener (MMS) (Le & Muñoz, 1998) to assess for history of MDD and current MDD. The MMS is a self-report checklist that assesses MDD using DSM-V criteria. Previous research supports the MMS as a valid instrument for MDD screening (Vasquez et al., 2008). Women meeting MDD criteria who are not currently in treatment will be referred to the supervisor at their HV agency.

During any of the research assessments, if the participant endorses current thoughts of harming herself or others, the following protocol should be followed, and documented on an Incident Report.

Maternal Mood Screener (MMS), Question 9d

→ *In the past 2 weeks, subject endorses she has attempted suicide in the past two weeks*

The Quick Inventory of Depressive Symptomatology (QIDS), Question 12

→ *In the past week, subject selects answer #3 (I thought of suicide or death several times a day in some detail, or I made specific plans for suicide or actually tried to take my life)*

The Edinburgh Postnatal Depression Scale (EPDS), Question 10

→ *In the past week, subject endorses thoughts of harming herself quite often*

When assessments are completed over the phone or online during regular business hours the following protocol will be completed within 24 hours.

Within 24 hours of the study participant's completion of their assessments a member of the Research team will call the study participant and will let the participant know that he/she will be contacting their home visiting program to let them know about the difficulties they are having with thoughts about death/suicide/hurting yourself/others, so they can reach out and offer support. The research team member will ask the study participant the following questions:

- "Are you thinking about killing yourself?"
- "Have you ever tried to hurt yourself before?"
- "Have you thought of ways that you might hurt yourself?"
- "Do you have pills/weapons in the house?"
- "Do you think you might try to hurt yourself today?"
 - If her response is Yes, then call 911 and stay on the phone with her until help arrives

All individuals that complete the above surveys will receive the following resources immediately upon answering the above answer choices on the noted assessments

- ✓ Home Visiting Program Office phone number
- ✓ National Suicide Prevention Hotline (24/7)
 - [name] ([name])
 - <http://www.suicidepreventionlifeline.org/> (online chat available 24/7: "Lifeline Chat")

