Specific Aim #2 is to conduct a non-inferiority trial that compares the effectiveness of MB delivered by (a) mental health clinicians versus (b) paraprofessional home visitors.

Specific Aim #3 is to evaluate whether effectiveness of the two versions of MB (clinician led vs. paraprofessional home visitor led) varies according to patient characteristics (e.g., race, ethnicity, first-time mother, and/or geographic type of home visiting (HV) program (i.e., urban vs. rural).

Specific Aim #4 is to examine the feasibility and acceptability of MB delivered by paraprofessional home visitors and mental health clinicians.

Study time points include: baseline, immediately following the intervention period (or roughly eight weeks post enrollment for controls), 12 weeks postpartum, and 24 weeks postpartum. Primary time point of interest will be 24 weeks postpartum. This analysis plan will focus on the primary results manuscript, and thus, we will focus on Aims #1-#3.

Study Outcomes

Primary Outcome

Primary outcome of interest for Aims #1-#3 will be the Quick Inventory of Depressive Symptoms (QIDS-SR16) score as determined by participant self-report at 24 weeks postpartum. We will control for baseline QIDS-SR16 score. This is a continuous measure ranging from zero to 27 points, where higher scores signify increased depressive symptoms. QIDS-SR16 translates into depressive categories such that a score of less than five points indicates no depression, a score ranging from six to 10 indicates mild depression, 11-15 signifies moderate depression, 16-20

indicates severe depression, and anything above 20 would be labeled as very severe (<http://www.ids-qids.org/>). As a result, we deem a five-unit change or difference in score to be meaningful (as a jump in five points would result in an increase in depression severity tier for any individual patient).

Secondary Outcomes

The following secondary outcomes will further be examined in order to address subcomponents of specific aims and also to address some of the exploratory aims. These secondary outcomes align with key components of the Mothers and Babies intervention.

1. Incidence of major/clinical depression (major depressive episode [MDE])
 - a. A major depressive episode will be defined via the Maternal Mood Screener
 - b. MDE for the purposes of this study is defined as:
 - i. The participant indicates at least **five** of the problems listed within the past two weeks (part B on the form), **and**

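### The SAP outcome labelled incidence of major depressive episode (MDE) measures current MDE at each survey and is not limited to women without MDE at baseline

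*SAP*

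**What the plan says.** **Purpose.** Protocol 1.0 says that interventions which can be delivered through home visiting are needed to "prevent the onset of major depression and worsening of depressive symptoms among perinatal women". The power analysis in Protocol 14.0 discusses the "incidence of new cases of major depression".

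**Definition.** SAP, Secondary Outcomes, item 1 is "Incidence of major/clinical depression (major depressive episode [MDE])". The SAP states that "A major depressive episode will be defined via the Maternal Mood Screener". A case needs at least five "of the problems listed within the past two weeks (part B on the form"), one of them a core symptom, plus a yes to the interference question.

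**Schedule.** Protocol Table 4 lists the MMS as "Current & Lifetime Major Depressive Episode", at baseline, 12 weeks and 24 weeks postpartum. The post-intervention cell is empty, and Protocol 4.0 explains why: "The post-intervention assessment consists of one depressive symptom measure, so no remuneration will be provided". Table 4 shows that this one measure is the QIDS.

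**Analysis.** SAP, Statistical Methods, refers to depression onset as an example of a binary outcome and gives it a logit link and binomial distribution. It states no rule for combining visits or dating onset.

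**At-risk group.** SAP, Demographics and Baseline Assessments, item 3 defines women at risk as those not meeting MDE criteria at baseline. The parenthetical in Statistical Methods says the reverse: it excludes women who do not meet the criteria.

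**Shell.** SAP shell Table 2 has Incidence MDE rows at baseline, post-intervention, week 12 and week 24.

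**The concern.** Incidence counts new cases among people who did not have the condition at the start. The outcome as written counts everyone who meets criteria in the two weeks before a survey. It therefore includes women whose baseline episode has continued, and it leaves out women who became depressed and recovered between surveys.

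The label matters because prevention of onset is the rationale for the programme, and this is the outcome that would be read as measuring it. Current MDE depends on how often episodes start and on how long they last. A lower proportion in an intervention arm could come from either, and reporting it as lower incidence would attribute it to onset alone.

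The reversed parenthetical adds to the problem. Taken literally, the at-risk analysis would keep only women who already have MDE at baseline, among whom no first new case can be counted.

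**Working it through.** **1. Is the outcome incidence or prevalence?**

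- Look-back: two weeks (SAP item 1).
- MMS occasions after baseline: 12 and 24 weeks postpartum (Protocol Table 4).
- Restriction to women without baseline MDE: none for this outcome. At-risk status is a model covariate, and the at-risk subset analysis is described alongside the QIDS model with its definition reversed.
- A baseline incidence row can only be prevalence, and a post-intervention MDE row has no scheduled MMS behind it.

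Together these describe current MDE at each visit.

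**2. Which episodes are missed?** The documents give neither episode length nor onset pattern, so the following are assumptions: delivery at 40 weeks, baseline at entry, onset uniform from baseline to 24 weeks postpartum, fixed length D weeks, and any overlap with a look-back counted as caught.

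Let G be the weeks from baseline to the 12-week survey, G = (40 − gestation at entry) + 12. Entry at 33 weeks gives G = 19, at 26 weeks G = 26, and at 20 weeks G = 32. Follow-up is G + 12 weeks. An episode is missed if it ends before the look-back that closes its interval:

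missed share = [max(0, G − 2 − D) + max(0, 10 − D)] / (G + 12)

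For postpartum onsets only, it is 2 × max(0, 10 − D) / 24.

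| D (weeks) | Entry 33 wk | Entry 26 wk | Entry 20 wk | Postpartum onsets only |
|---|---|---|---|---|
| 4 | (13+6)/31 = 61% | 26/38 = 68% | 32/44 = 73% | 12/24 = 50% |
| 8 | (9+2)/31 = 35% | 18/38 = 47% | 24/44 = 55% | 4/24 = 17% |
| 12 | 5/31 = 16% | 12/38 = 32% | 18/44 = 41% | 0% |
| 16 | 1/31 = 3% | 8/38 = 21% | 14/44 = 32% | 0% |
| 24 | 0% | 0% | 6/44 = 14% | 0% |

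Counting any overlap as caught is generous. If an episode must fill the whole look-back, the entry-33 column becomes 87%, 61%, 35%, 16% and 6%.

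**3. A second duration model.** Let length be 2 weeks plus an exponential tail with mean μ. Then

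detected share = [μ(1 − e^(−(G−4)/μ)) + 4 + μ(1 − e^(−8/μ)) + 4] / (G + 12)

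For mean lengths of 8, 13 and 26 weeks (μ = 6, 11, 24), detection is 58%, 71% and 84% at entry 33 weeks, and 48%, 61% and 77% at entry 26 weeks. For postpartum onsets only it is 70%, 81% and 90%.

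**4. Consequence for power.** Protocol 14.0 states 64% power for 15% vs 20% with 612 per arm, ignoring the ICC. As a two-sided 5% test:

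- SE under no difference = √(2 × 0.175 × 0.825 / 612) = 0.02172
- SE under the alternative = √((0.15 × 0.85 + 0.20 × 0.80) / 612) = 0.02167
- Power = Φ[(0.05 − 1.96 × 0.02172) / 0.02167] = Φ(0.343) = 63.4%

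The stated figure reproduces. If 15% and 20% were cumulative rates and the surveys captured the same fraction in both arms:

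- 80% captured: 12% vs 16%, power 52%
- 60% captured: 9% vs 12%, power 40%

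These use the Protocol's 612 per arm. The SAP now plans 16 × 23 = 368 per arm, so absolute power is lower still.

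**The case against.** Two-week MDE at fixed visits is a legitimate secondary endpoint. The primary outcome is the 24-week QIDS score, and Aims 1 and 2 do not name MDE onset. Protocol 14.0 already says that non-inferiority on MDD incidence is not expected to be claimable. The QIDS is collected post-intervention in all arms, so symptoms in late pregnancy are observed even though MDE status is not. The SAP adjusts for baseline MDE status, and it says its table shells are not binding. All of this stands. It limits the importance of the point, but adjustment is not restriction, and none of it makes the defined quantity an incidence.

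A reader might infer more than the documents support:

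- **That a known share of onsets is lost, such as a quarter to a half.** That depends on assumed durations, entry time and onset pattern. Across the fixed-length scenarios at entry 33 weeks it runs from 0% to 61%, and postpartum onsets are caught more often.
- **That because the look-backs cover 4 of 31 weeks, only 13% of onsets are seen.** Calendar coverage is not detection; an episode still present at a survey is caught.
- **That the definition favours an arm or makes the two MB arms look alike.** Nothing in the documents shows capture differing by arm.
- **That the missing episodes can be recovered from the MMS.** Table 4 mentions lifetime MDE, and Protocol 15.0 says the MMS is used "to assess for history of MDD and current MDD". The form is not shown, so whether it can date an episode to the interval between surveys is unknown.

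**Conclusion.** The labelling error is firm, because it follows directly from the definition, the schedule and the shell. Followed as written, the plan would report current MDE at each survey, in women with and without baseline MDE, under the names incidence and onset.

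The size of the loss is not firm. It is large for short episodes and early entry, and small or nil for long episodes and for most postpartum onsets. If capture is the same in all arms, the consequence is a smaller absolute difference and less power (63% falling to 52% or 40% in the illustration above), with no bias toward either arm. The primary analysis is unaffected.

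The correction is still worth making, because it decides whether the trial may claim that it prevented new episodes.

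**What to change.** In the SAP:

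1. **New MDE.** Among women not meeting MDE criteria at baseline, define new MDE as part B criteria met at 12 or 24 weeks postpartum. Describe it as new MDE detected at one of those surveys, not as all onsets. State how a woman with only one of the two surveys is handled.
2. **At-risk group.** Correct the parenthetical in Statistical Methods to agree with item 3 of the baseline covariates.
3. **All participants.** Label this analysis current MDE at 12 and at 24 weeks postpartum, and bring the onset wording in Statistical Methods into line.
4. **Shell Table 2.** Remove the baseline incidence row and the post-intervention MDE row. Baseline MDE already appears in shell Table 1.
5. **Lifetime section.** Use it only as a sensitivity definition, and only if the form as already administered can date an episode to the interval since the last survey. Do not change the recall stem now: the SAP reports all three randomization waves done and 29 intervention sites with at least one cohort implemented. A change could not recover women already surveyed and would mix definitions.

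The cost is SAP wording and one derived variable; no new data or visits are needed. The prevention claim becomes narrower, and the at-risk analysis has a somewhat smaller sample.

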 - ii. **At least one** of the problems must be: symptom 1 (feeling depressed) or symptom 2 (losing interest or pleasure), **and**
 - iii. The participant indicates '**yes**' to the question: *Did these problems interfere with your life or activities a lot?*
2. Behavioral activation scale score (BA)
3. Social support (due to the highly skewed nature of this outcome, we dichotomized it into ≥ 4 versus <4).
4. Mood regulation
5. Decentering
6. Mental health service utilization (i.e., an indicator for whether participants are enrolled in therapy with a counselor and/or currently taking antidepressants). This outcome may be explored in greater detail in a separate paper; however, we plan to examine the difference between arms controlling for baseline mental health service utilization.

Tertiary Outcomes (the following will be explored in a separate paper from the primary results)

1. Pleasant activities
2. Perceived stress
3. Parental cognitions and conduct toward the infant scale
4. Dyadic adjustment scale
5. Flourishing scale
6. Prenatal health behaviors

The outcomes above are tied to validated scales with specific scoring requirements. The scoring instructions will be followed and analyses will proceed on the final, scored variables. In addition, we plan to summarize '**dosage**' of intervention in the active intervention arms as the number of sessions attended (out of six possible). We will also summarize the number of participants that were '**compliant**', which is defined as attending **at least four of the six sessions**.

Demographics and Baseline Assessments

The following are specific demographic/baseline assessments of interest for analyses. Primary analyses will adjust for these covariates as we anticipate they will influence outcome. We plan to report both adjusted and unadjusted intervention effect estimates:

1. Race/ethnicity (at the participant level): minority vs. not belonging to a minority category.
2. Whether participant is a first-time mother (i.e., current number of children = 0 at baseline).
3. Currently at risk for depressive episode (i.e., those NOT meeting criteria for MDE at baseline).

4. Primary language of intervention receipt (for MH and HV arms) or primary language in which the participant completed assessments (for control arm).
5. Education: at least some college vs. less than college.

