4. Of those that meet acceptable levels of imbalance, we randomly select one allocation for use in the current study.

We chose the p-value corresponding to the Kruskal-Wallis test (nonparametric version of an Analysis of Variance [ANOVA]) as our criterion for 'balance' in step #3 above. If the p-value for each of the three variables is larger than 0.30 for a given simulated allocation scheme, that particular allocation is deemed 'acceptable'. This criterion is adapted from the 'Minimal Sufficient Balance' principle from Zhao et al. [3] in the individual sequential randomization literature.

In the current study, randomization occurred in three waves for logistical purposes. The first included 14 sites (2 C:6 HV:6 MH); the second included 19 sites (4 C:7 MH:8 HV); allocation ratio was slightly off in this wave to account for dropout sites); and the third wave included 12 sites (1 C:6 MH:5 HV). Thus, we randomized a total of 45 sites in three waves; randomization of 42 sites was the study goal, reflected in our approved research plan. However, to account for site dropping out in the meantime, we adapted the algorithm to increase the number of sites randomized and also to allow for slightly discrepant allocation ratios than the planned 1:3:3 within each wave.

After randomization, eight programs dropped out, thereby yielding a total of 37 study sites contributing data for analyses. Data collected from all study participants will be used in the analysis. Among the 37 active study sites, 16 HV programs received the MB intervention delivered by mental health professionals, 15 received MB intervention delivered by HV paraprofessionals, and six programs serve as control sites. As an aside, 29 intervention sites ended up implementing at least one cohort (15 MH, 14 HV).

Statistical Methods

Descriptive statistics will summarize baseline characteristics (both site-level and participant-level) overall and by arm. As appropriate, mean \pm standard deviation (or median [inner quartile range]) will be used in cases of skewed or non-normal empirical distributions) and frequency (proportions) will summarize continuous and categorical data, respectively. Analyses will employ normal theory methodology as appropriate, and in cases of violations of assumptions, transformations and/or nonparametric analyses may be utilized.

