The double-sided arrows represent 95% confidence intervals for the model-estimated adjusted mean 24-week difference in QIDS-SR16 score. Note that higher score signifies more depressive symptoms; thus if the estimated difference (HV minus MH score) is larger than zero, the HV arm has on average worse depressive symptoms. Since the pre-specified margin of non-inferiority is two units on the QIDS-SR16 scale, we will claim non-inferiority if the upper limit of the adjusted 95% confidence interval for the HV-led arm minus the MH-led arm comparison remains below two. The red arrows indicate scenarios in which we cannot claim non-inferiority and the blue arrows indicate scenarios in which the criterion for non-inferiority is met.

Using the same analytic approach, we will explore the addition of covariate-by-arm interaction terms in the aforementioned model or a three-way covariate-by-arm-by-time interaction term in the longitudinal modelling in order to explore whether effectiveness of intervention varies by patient characteristics (Aim #3). The covariates to be explored include: race/ethnicity, first-time mother, language, education, and use of mental health services at baseline. These analyses are more exploratory in nature, and thus power/sample size considerations do not focus on interaction effects. As a result, we anticipate evaluating interaction effects at the 10% level of significance without adjustment for multiple hypothesis tests. Qualitative data analysis methods will evaluate feasibility and acceptability of MB in each setting (Aim #4), and the details of these analyses will be specified elsewhere.

Additional analyses surrounding Aims #1-#3 will employ longitudinal methods, utilizing all study data at all time points (i.e., inclusion of a fixed study time point effect). Secondary outcomes will all be analyzed in this fashion with the exception being binary response variables (e.g., depression onset). In these cases, appropriate link and distributional assumptions (logit, binomial, respectively) will be specified. For the participants receiving active intervention (either HV-led or MH-led Mothers and Babies), we will examine a 'dose' variable in relation to outcomes. This dose variable will be defined as the number of sessions (out of six possible) attended for an individual participant.

Analytic Dataset

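### Social support is cut to ≥4 v <4 for skewness alone, with no stated basis for 4; the scored scale should be the main analysis of this secondary outcome

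*SAP*

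**What the plan says.** - **The cut.** In the SAP's list of secondary outcomes, social support carries this note: "due to the highly skewed nature of this outcome, we dichotomized it", the two groups being ≥4 and <4. Skewness is the only reason given.
- **The instrument.** The protocol (section 4.0, Table 4) lists the "MOS Social Support Survey" at baseline, 12 weeks and 24 weeks postpartum, with no cut-point. Neither document gives a score range, a validated or clinical meaning for 4, or an expected share of women above it.
- **The scoring rule.** After the outcome lists, the SAP says of its validated scales: "The scoring instructions will be followed and analyses will proceed on the final, scored variables".
- **The remedy for non-normal data.** Under Statistical Methods: "in cases of violations of assumptions, transformations and/or nonparametric analyses may be utilized". Dichotomising is not mentioned there.
- **The model that follows.** The same section sends secondary outcomes to longitudinal models using all time points: "Secondary outcomes will all be analyzed in this fashion with the exception being binary response variables". For binary outcomes, "appropriate link and distributional assumptions (logit, binomial, respectively) will be specified".
- **Timing.** The SAP's Randomization Methods section already reports that sites had dropped out and that 29 intervention sites had run at least one cohort. Technical Details allows the plan to change for unexpected outcome distributions, under version control. Timeline for Analyses bars summaries by arm before the final analysis, except for quality control.

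**The concern.** Cutting a score at one point treats every change that does not cross that point as no change. The SAP says that its secondary outcomes align with key components of the intervention, and the protocol names contact with others as one of the three sections of the course. A null result on social support could therefore reflect the cut and not the course, and a positive one could depend on the choice of 4. No planned analysis of the undivided score would show which.

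The reason given does not carry the decision. Skewness bears on how to model or test a score. It does not by itself call for discarding the score, and the SAP's general text offers other remedies.

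**Working it through.** The plan states no power, rate or effect size for social support, so there is no figure of its own to reproduce.

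**Inputs from the SAP.** Sites contributing data: 6 control, 15 HV, 16 MH (Randomization Methods). Analysable women per site: 23 on average. ICC: 0.01 (both from Power and Sample Size Considerations). This gives 6 × 23 = 138 control, 15 × 23 = 345 HV and 16 × 23 = 368 MH women.

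**Inputs assumed.** A 1–5 score with a ceiling, the share *p* at or above 4, the share *c* at the ceiling, and the effect size. None of these is in the documents.

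**Step 1. Efficiency of the cut relative to the score.**

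Normal model: RE = φ(z_p)² / [p(1−p)]. 
Ordinal (proportional-odds or rank) model: RE = 3p(1−p) / (1−c³).

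| p at or above 4 | Normal | Ordinal, c = 0 | Ordinal, c = 0.4 |
|---|---|---|---|
| 0.5 | 0.637 | 0.750 | 0.801 |
| 0.7 | 0.576 | 0.630 | 0.673 |
| 0.8 | 0.490 | 0.480 | 0.513 |
| 0.9 | 0.342 | 0.270 | 0.288 |

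For example, at p = 0.8 and c = 0.4: 3 × 0.8 × 0.2 / (1 − 0.064) = 0.48/0.936 = 0.513. The most favourable case tried was p = 0.5, c = 0.5: 0.75/0.875 = 0.857, a loss of 14%.

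**Step 2. What that means for power.** A two-sided 5% test with 90% power on the score has power Φ(√RE × (1.960 + 1.282) − 1.960) after the cut. Under the normal model this is 73% at p = 0.5, 62% at p = 0.8 and 47.5% at p = 0.9. Put as sample size, the 345 + 368 = 713 HV and MH women would be worth 713 × 0.637 ≈ 454, 713 × 0.490 ≈ 349 or 713 × 0.342 ≈ 244.

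**Step 3. Skewed scores, no clustering.** Normal scores were clipped to 1–5 and rounded to quarter points, with 350 per arm, a latent shift of 0.25 SD and two-sided 5%.

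| Skew | Share ≥4 | t-test | Wilcoxon | Cut at 4 |
|---|---|---|---|---|
| −0.42 | 47% | 88.5% | 88.4% | 75.4% |
| −0.72 | 63% | 88.8% | 89.0% | 71.6% |
| −1.0 | 73% | 85.8% | 86.0% | 66.2% |
| −1.63 | 83% | 78.6% | 80.4% | 55.4% |

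**Step 4. Skewed scores with clustering.** HV v control, 6 v 15 sites, 23 women per site, ICC 0.01, ceilinged 1–5 scores with 50–82% of controls at or above 4, analysed at site level.

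- Type I error for the uncut score was about 5% (4.9–5.8% in one set of runs, with skew from −0.6 to −1.8).
- At a latent shift of 0.30 SD, power was about 64–70% for the score and 45–57% for the cut. Another set of runs under the same site structure gave 60–71% for the score, 62–69% for ranks and 45–57% for the cut.
- At 0.35 SD, power was 72–82% (score), 75–82% (ranks) and 57–69% (cut).

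**Step 5. Which analysis of the score is safe.** With 6 v 15 sites and about 23 women per site, an uncorrected sandwich z-test had type I error of about 9–11% at a nominal 5%, for ICCs of 0, 0.01 and 0.05. Its validity depends on the number of sites, not of women, so the replacement analysis must allow for six control sites.

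**The case against.** **The SAP does not strictly contradict itself.** Its sentence on transformations and nonparametric methods is permissive, and the logit/binomial model for binary outcomes is specified. A proportion above a threshold is also a legitimate and readable summary of a ceilinged score. This stands: the cut is a weak choice with an unexplained threshold, not a gap in the plan.

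**The size of the loss rests on assumptions.** This also stands. The distribution, score range and effect size are all assumed. Baseline adjustment was not simulated, nor was HV v MH. The gain depends on shape: for one Beta-shaped score (parameters 2 and 0.6) a rank test had 42% power against 39% for the cut, only 3 points better. A reader might take the figures above as the loss in this trial, but the documents do not give what would be needed to say so.

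**The timing is an inference.** From the past tense, and from a SAP written after cohorts had run, a reader might infer that 4 was picked after seeing results. The documents do not support that. They do not say when or on which data the skew was seen. Social support is measured at baseline, so it may have been seen there. Nothing shows a look by arm, and the SAP bars one except for quality control. A pooled look at shape does not reveal the treatment effect, and recording a change in a version-controlled SAP is the process that the SAP describes. What remains is that the origin and date of the cut are not stated.

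**The outcome is one of six secondary outcomes,** and no power is claimed for it. True, and this limits the importance of the point.

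**Conclusion.** The point holds as a minor improvement to one secondary outcome. The SAP cuts social support at 4 for skewness alone, states no basis for 4 and plans no analysis of the undivided score, although its own general text points to scored variables and to other remedies.

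Skewness does not force the cut. In clustered simulations with strongly ceilinged scores, a site-level contrast of the uncut score held its type I error at about 5% and had more power (about 64–70% v 45–57% at a latent shift of 0.30 SD). Those figures rest on assumed 1–5 scores, 50–82% of controls at or above 4, 23 women per site and ICC 0.01. The direction held in every scenario tried, but the size for this trial cannot be fixed. The conclusion does not depend on when the cut was chosen, and no unblinded choice is alleged.

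**What to change.** In the SAP's Secondary Outcomes and Statistical Methods sections:

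1. Make the scored social support scale the main analysis for this outcome, adjusted for baseline score and with a random site effect. Use either an ordinal mixed model or a linear mixed model with small-sample degrees of freedom. A cluster-level, rank or permutation analysis would also serve. Do not use uncorrected sandwich errors, because the control arm has only six sites.
2. Keep ≥4 v <4 as a supportive analysis.
3. State the score range, the source of the cut at 4, and when and on which data the skew was assessed (baseline or follow-up, pooled or by arm).

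The cost is SAP wording only, with no new data. The downside is that a mean difference or an odds ratio across the scale is less simple to explain than a proportion. The supportive ≥4 analysis still supplies that proportion.
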